## PART B STUDY DESCRIPTION

TITLE OF PROTOCOL	A randomized, double blind, placebo-controlled study to evaluate the impact of a multi-strain synbiotic on fecal metagenomic stability, gut barrier integrity, and metabolic output of the gut microbiota in premenopausal adult females.
Principal Investigator	[name]

### B1. PURPOSE OF PROTOCOL

Irritable bowel syndrome (IBS) is a chronic functional gastrointestinal disorder that is commonly seen in clinical practice. Specifically, it is a functional bowel disorder that is thought to result from a disorder of gut–brain interaction. Though patients with IBS often have a heterogeneous symptom profile, the predominant theme is the presence of abdominal pain or discomfort that is usually relieved by defecation. Genetic background and environmental factors are important in the pathogenesis of IBS, but the precise cause of IBS is still unknown.

Probiotics are live microorganisms with a vast array of therapeutic potential for gastrointestinal disease. Several probiotics strains have shown beneficial outcomes in constipation-predominant IBS (IBS-C) patients, especially as an adjunct to conventional treatment. However, a number of controversial issues regarding the roles of probiotics in pathogenesis of IBS-C remain to be clarified, including precise mechanism of action.

This protocol aims to assess the impact of a mix of 24-beneficial strains on fecal metagenomic stability and individual gastrointestinal symptoms specifically in a cohort of subjects with IBS-C or IBS-M.

### B2. SIGNIFICANCE AND BACKGROUND FOR THE STUDY

The study agent is a 24-strain cocktail of live microorganisms (Seed Health Inc.). Seed Health Inc. is providing the consortia of probiotics, whose individual ingredients carry the designation Generally Recognized as Safe (GRAS) by the US FDA, which is a designation applied to all food ingredients. The live microorganisms included are: *Bifidobacterium breve* SD-BR3-IT, *Lactobacillus rhamnosus* SD-LR6-IT, *Lactobacillus plantarum* SD-LP1-IT, *Bifidobacterium longum* SD-BB536-JP, *Lactobacillus reuteri* SD-LRE2-IT, *Bifidobacterium infantis* SD-M63-JP, *Lactobacillus rhamnosus* HRVD113-US, *Bifidobacterium lactis* HRVD574-US, *Bifidobacterium breve* HRVD521-US, *Lactobacillus casei* HRVD300-US, *Bifidobacterium longum* HRVD90b-US, *Bifidobacterium lactis* SD-BS5-IT, *Bifidobacterium lactis* SD150-BE, *Lactobacillus rhamnosus* SD-GG-BE, *Lactobacillus reuteri* RD830-FR, *Bifidobacterium adolescentis* SD-BA5-IT, *Lactobacillus crispatus* SD-LCR01-IT, *Lactobacillus salivarius* SD-CRL1328-IT, *Lactobacillus fermentum* SD-LF8-IT, *Bifidobacterium longum* SD-CECT7347-SP, *Lactobacillus casei* SD-CECT9104-SP, *Bifidobacterium lactis* SD-CECT8145-SP, *Lactobacillus plantarum* SD-LDL400-UK, *Bifidobacterium lactis* SD-MB2409-IT. Prebiotic extracts *Punica granatum*, *Inonotus obliquus* and *Pinus sylvestris* are also included in the capsules.

Previous studies performed on individual live microorganisms in the Seed Health inc. synbiotic have shown significant improvement in multiple markers of digestive health intestinal transit time, ease of expulsion, bloating, discomfort and stool consistency. After 2 weeks of supplementation with *Bifidobacterium longum* BB536, healthy adults suffering from constipation experienced an increase in defecation frequency, alongside changes in fecal color, volume and shape. Lower concentrations of ammonia production were also reported during the period of *B. longum* BB536 administration. In addition to changes in fecal enzymes, which are important for controlling the amount of fecal putrefactive substances, a study in 110 healthy volunteers (50 males and 60 females) treated with *Lactobacillus plantarum* LP01 and *Bifidobacterium breve* BR03, reported that probiotic supplementation significantly improved the number of weekly bowel movements and symptoms associated with evacuations (consistency of feces and ease of expulsion); Abdominal bloating and anal itching-burning or pain- was also improved with probiotic use. The synbiotic also contains a number of strains that protect gut barrier integrity: *B. breve* BR3, *B. longum* BB-536, *Lactobacillus rhamnosus* GG, *Lactobacillus salivarius* LS1, *Lactobacillus casei*, *Lactobacillus rhamnosus*, *Bifidobacterium lactis*, *Bifidobacterium breve*, *Bifidobacterium longum*. *B. breve* BR3 and *L. salivarius* LS1 have been clinically shown to improve gut barrier function by reducing bacterial translocation as measured by fecal LPS in almost 100 men and women with

atopic dermatitis.

The following studies were completed with individual strains:

- *Lactobacillus plantarum* LP01 (LMG P-21021), *Bifidobacterium breve* BR03 (DSM 16604) or *Bifidobacterium animalis* subspecies *lactis* BS01 (LMG P-21384):

Over a period of 5 years (2003 to 2008), the study involved 300 healthy volunteers (151 males and 149 females; age 24 to 71 y) with evacuation disorders and hard stools. Subjects were divided into 3 groups: 80 subjects in the group A received placebo, 110 subjects in the group B received mixed *L. plantarum* LP01 and *B. breve* BR03 (2.5 billion colony-forming units/day of each strain), and 110 subjects in the group C received *B. animalis* subspecies *lactis* BS01 (2.5 billion colony-forming units/day) daily for 30 days (T30). Subjects were assessed at 15 (T15) and 30 days (T30) of supplementation. A statistically significant difference was recorded at T15 and T30 versus T0 both in group B (T15 vs. T0  $P < 0.001$ ; T30 vs. T0  $P < 0.001$ ) and in group C (T15 vs. T0  $P < 0.001$ ; T30 vs. T0  $P < 0.001$ ). No differences were observed in the placebo-control group (T15 vs. T0  $P = 0.148$ ; T30 vs. T0  $P = 0.507$ ). These differences were reflected in the number of weekly evacuations but similar statistically significant improvements were observed with consistency of feces, ease of expulsion, sensation of complete emptying, anal itching, burning or pain and also abdominal bloating.

- *Lactobacillus plantarum* LP01 and *Bifidobacterium breve* BR0:

Study involved 50 patients (24 males, 26 females) (mean age range = 26–64 years) with IBS according to Rome II criteria. Patients were randomly assigned to receive either the active preparation containing *Lactobacillus Plantarum* LP01 and *Bifidobacterium Breve* BR0 (5 billion colony-forming units) or placebo powder containing starch identical to the study product once daily for 4 weeks. Pain score in different abdominal locations after treatment decreased in probiotics group of 38% versus 18% ( $P < 0.05$ ) of placebo group after 14 days and of 52% versus 11% ( $P < 0.001$ ) after 28 days. The severity score of characteristic IBS symptoms significantly decreased in probiotic group versus placebo group after 14 days 49.6% versus 9.9% ( $P < 0.001$ ) and these data were confirmed after 28 days (44.4% versus 8.5%,  $P < 0.001$ ).

- *Bifidobacterium longum* BB536:

*Bifidobacterium longum* BB536 was administered to 40 healthy adult female volunteers and the effects on defecation frequency and fecal characteristics were assessed. They were administered BB536 (2 billion colony-forming units) daily in 200 ml of milk for three weeks. (Milk was used as the control diet). The defecation frequency of volunteers in the interval period was  $0.54 \pm 0.18$  times per day. They suffered constipation slightly. The frequency increased to  $0.65 \pm 0.21$  and  $0.72 \pm 0.22$  after ingesting milk and BB536 milk, respectively. These increases were statistically significant when compared with the interval period ( $p < 0.001$ ).

### B3. DESCRIPTION OF RESEARCH PROTOCOL

#### A. Study Design – Overview, Methods, Procedures

##### Study Design

This is a 1:1 randomized, double blind 12-week comparison of effects of SH-DS01 by Seed Health Inc. versus placebo, in a cohort of 100 women with IBS with constipation or IBS with mixed bowel habits. 50 IBS-C or IBS-M patients will receive the daily synbiotic for 12 weeks, while 50 IBS-C or IBS-M patients will receive the placebo.

- **Initial Screening Session (1 hour)** – The purpose of this screening is to determine if the subject meets the qualifications to participate in the research study. After the screening is complete they will be notified whether they meet qualification or not. If the subjects qualify they will be provided with the supplementation and instructions for future study appointments. Informed Consent: This will be explained by a member of the study staff in an individual setting. After it has been explained and all questions have been answered, the subject will be asked to sign the consent form.

- Brief Medical History Form: After completing this short survey, the medical history will be reviewed and either approval will be issued to continue with the study or exclusion from further participation.
- Physical Exam:
  - Measurement of Height, Weight: the subject will be asked to remove shoes and any items in pockets (i.e. loose change, wallet, watch, cell phone, etc.) prior to having height (stadiometer) and weight (digital scale) measured.
- Medical history and interval history to include current medications, recording of adverse events (including intercurrent illness and any new diagnoses).
- Other Vital Signs: Temperature, Heart Rate, Blood Pressure
- **Study Procedures for Qualified Participants:** If the subject meets the study requirements and is cleared for study enrollment they will be asked to complete the following tasks:
  - **Pre-supplement wash-out (1 week):** during which the participant is to stop taking probiotics or antibiotics, in order to eliminate any residual effects of the synbiotic intervention. During this period, subjects will be provided with a single blinded placebo. Participants who are judged to be “responders” will be excluded from further participation in the trial.

**Visit 2 (Single-Blind Placebo Run-In)**

- **Symptom assessment; questionnaires.**
- **Vital Signs:** Weight, Heart Rate, Blood Pressure.
- **Single-Blind Placebo:** Subjects will be provided with a single-blind placebo for a period of 28 days pre-randomization
- **Urine Pregnancy Test**

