**Visit 3 (Randomization)**

- **Vital Signs:** Weight, Heart Rate, Blood Pressure.
- **Symptom assessment; questionnaires.**
- **Physical Examination**
- **Blood Collection:** General laboratory tests such as complete blood count (CBC) will be performed for all study subjects prior to randomization to ensure the safe and appropriate treatment of subjects. Clinical laboratory tests will be overseen by the PI or a physician sub-investigator. Functional analysis of serum and cells will be measured to look at LPS-binding protein, C-reactive protein (CRP) and a cytokine panel. Serum and cells will be used or banked for translational/mechanistic studies.
- **Stool Sample Collection:** Subject will be provided with a take-home stool collection kit to collect stool samples.
- **Assess pill count:** If pill count from run-in indicates <80% adherence/compliance, subject will not be randomized
- **Randomization:** Subject will be randomized into double-blind portion of the study. Subjects will be given enough study medication to last until next visit.

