**C. Subject Selection****Inclusion criteria**

1. Patient must be willing and able to give informed assent/ consent for participation in the study
2. Patient must be willing and able (in the PI's opinion) to comply with all study requirements.
3. Patient must be a premenopausal female over the age of 18.
4. Patient must have a documented history of IBS that is not completely controlled by current IBS drugs.
5. Patient must have a score of  $\geq 150$  on the IBS-SSS at screening.
6. Patient must have no clinically relevant (in the judgment of the PI) abnormal blood laboratory levels at screening or randomization.
7. The clinician will assess eligibility as per the Rome IV criteria (Recurrent abdominal pain or discomfort at least 1 day/week in the last 3 months associated with two or more of the following: Improvement with defecation. Onset associated with a change in frequency of stool).

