**Exclusion criteria**

1. Patient has clinically significant unstable medical conditions other than IBS.
2. Patient has had clinically relevant symptoms or a clinically significant illness in the four weeks prior to screening or randomization.
3. Patient has clinically significant laboratory values (in the PI's opinion).
4. Patient has a history or presence of alcohol or substance abuse within the last two years prior to the study or daily consumption of five or more alcohol-containing beverages.
5. Patient is currently using or has in the past used recreational or medicinal cannabis, or synthetic cannabinoid based medications (including Sativex®) or supplements (including hemp oil/extracts) within one month prior to study entry and is unwilling to abstain for the duration for the study.

6. Patient has consumed any probiotic product three days prior to screening and/or is unwilling to abstain from consuming these during the study.
7. Intake of antibiotics in the past 1-month (i.e. penicillin, amoxicillin, cephalexin (Keflex), erythromycin (E-Mycin), clarithromycin (Biaxin), azithromycin (Zithromax), ciprofloxacin (Cipro), levofloxacin (Levaquin), ofloxacin (Floxin), co-trimoxazole (Bactrim), trimethoprim (Proloprim), tetracycline (Sumycin or Panmycin), doxycycline (Vibramycin), gentamicin (Garamycin), or tobramycin (Tobrex). The supplement in the present study may have a minor interaction with these medications.
8. Patient has any known or suspected hypersensitivity to pomegranate, pine, or mushrooms, or any of the excipients of the Supplement Synbiotic Product (SSP).
9. Patients of child bearing potential unless willing to ensure that they use effective contraception, for example, oral contraception, double barrier, intra-uterine device, during the study and for three months thereafter.
10. Patients who are pregnant, lactating, or planning pregnancy during the course of the study and for three months thereafter.
11. Patients who have been part of a clinical trial involving any investigational product in the previous six months.
12. Any other significant disease or disorder which, in the opinion of the PI, may either put the patient at risk because of may either put the patient at risk because of participation in the study, may influence the result of the study, or affect the patient's ability to participate in the study.

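### The only pregnancy test in the visit schedule comes 28 days before randomisation, so pregnancy status is not checked when double-blind product is first dispensed

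*Combined protocol and SAP*

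**What the plan says.** Inclusion criterion 3 reads "Patient must be a premenopausal female over the age of 18", so pregnancy is a possibility to be considered throughout the trial. Exclusion criterion 10 bars "Patients who are pregnant, lactating, or planning pregnancy during the course of the study and for three months thereafter". Exclusion criterion 9 excludes "Patients of child bearing potential unless willing to ensure that they use effective contraception", for the length of the study and three months afterwards.

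In section B3.A, the list for Visit 2 (Single-Blind Placebo Run-In) contains the item "Urine Pregnancy Test". The same list sets the length of the run-in: "Subjects will be provided with a single-blind placebo for a period of 28 days pre-randomization".

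The list for Visit 3 (Randomization) covers vital signs, questionnaires, a physical examination, blood collection, a stool kit and a pill count. On bloods it says "General laboratory tests such as complete blood count (CBC) will be performed for all study subjects prior to randomization". On adherence it sets a stopping rule: "If pill count from run-in indicates <80% adherence/compliance, subject will not be randomized". It then says "Subject will be randomized into double-blind portion of the study", and study product is handed out. No pregnancy test is named at Visit 3, at screening, or at Visits 4, 5 or 6.

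**The concern.** The test is placed where it protects entry to the placebo run-in. None is specified at the point where half the women first receive the active product. Pregnancy status can change over four weeks, and the protocol treats it as a reason not to take part.

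The protocol already looks again at other matters that can change. Inclusion criterion 6 and exclusion criterion 2 both refer to randomisation as well as screening, and the pill count can stop randomisation on the day. Pregnancy is an explicit exclusion with no equivalent check.

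What is at stake is participant safety and correct eligibility. There is also a small analytic consequence. A pregnancy found before randomisation is a simple screen failure. One found afterwards belongs to a randomised woman, who stays in the intention-to-treat set and, if she leaves the study, is counted as a failure under Statistical Considerations.

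**Working it through.** The plan gives no figure on this point to reproduce. The check is a reading of the schedule, followed by a rough size under a stated assumption.

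**Schedule.**

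| Contact | Pregnancy test named | Product given |
|---|---|---|
| Screening | No | See the note on timing under the objection |
| Visit 2 | Yes, urine | Single-blind placebo, 28 days |
| Visit 3 | No | Double-blind synbiotic or placebo |
| Visit 4 (Day 42) | No | Double-blind product continued |
| Visit 5 (Day 84) | No | None listed |
| Visit 6 (Day 92, at home) | No | None listed |

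- Age of the only test result at randomisation: 28 days.
- Age of that result at the end of dosing: 28 + 84 = 112 days, with no repeat listed.

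**Size.** Inputs from the documents: 100 women, 1:1 allocation, so 50 on synbiotic; run-in of 28 days. Assumption, not from the documents: a fraction *r* of women using contraception conceive per 28 days, with *r* between 0.001 and 0.01. The figures count conceptions during the run-in only.

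- Annual equivalent over 13 periods of 28 days, 1 − (1 − *r*)^13: 1 − 0.999^13 = 0.013 and 1 − 0.99^13 = 0.122. About 12% a year is pessimistic for women using effective contraception.
- Expected number pregnant at randomisation, 100*r*: 0.1 to 1.0.
- Expected number of these on synbiotic, 50*r*: 0.05 to 0.5.
- Chance of at least one on synbiotic, 1 − (1 − *r*)^50: 1 − 0.999^50 = 0.049 and 1 − 0.99^50 = 0.395.

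For run-in conceptions at a given *r* these are upper bounds, because some women would notice and report a pregnancy before Visit 3.

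**The case against.** The strongest reply is that the remaining gap is narrow and the likely harm slight.

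- **Existing controls.** There is a test before the run-in, a contraception requirement, a bar on women planning pregnancy, and a physical examination and physician-overseen bloods at Visit 3. These lower the risk. None establishes pregnancy status on the day, and the sponsor tests at Visit 2 even though the same contraception rule already applies there.
- **Open-ended laboratory wording.** The blood count is given only as an example, so a pregnancy test at Visit 3 is not ruled out. But the test has its own line at Visit 2 and none at Visit 3, so staff have no instruction to do it.
- **Low hazard.** Section B2 describes the individual ingredients as GRAS, and section B5 lists only minor digestive effects and a rare allergy. This stands, and it limits the importance of the point. It does not remove the mismatch with an exclusion the sponsor chose to set.
- **Assumed rate.** The 39% rests on the pessimistic end of an assumption and should not drive the assessment. This stands; the finding itself rests on the schedule.
- **Unclear timing.** The Study Design section also describes a one-week wash-out on single-blind placebo and says qualifying women receive the supplementation after screening. If one week were the true interval, *r* would fall about fourfold and the expected number on synbiotic would be 0.05/4 to 0.5/4, or about 0.01 to 0.13. The 28 days at Visit 2 is the explicit statement, and on either reading Visit 3 names no test.
- **Limited reach of the remedy.** At the same constant rate, conceptions over 84 days of dosing would be three times those in the run-in (84/28 = 3), or 0.15 to 1.5 in the synbiotic arm. A Visit 3 test therefore reaches at most 28/112 = 25% of potentially exposed pregnancies, and fewer if a very recent conception tests negative. This stands as a limit on the safety benefit. It does not touch the eligibility argument, which concerns status at randomisation.

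**Conclusion.** The concern holds. The only named test is 28 days old when double-blind product is first dispensed, and the visit lists, followed as written, can give the synbiotic to a woman the protocol excludes.

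Under the assumed conception rates the expected number is well below one woman in the synbiotic arm, with a chance of at least one between about 5% and 39%; the lower part of that range is the more plausible. No pregnancy-specific hazard is stated, so expected harm is small, and the effect on power and error rates is negligible. The change is worth making because it closes a real gap in verifying eligibility at very little cost. That the gap exists is clear from the text. Its size is uncertain, because it depends on a rate the documents do not give.

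**What to change.** Add a urine pregnancy test to the Visit 3 list, with a negative result required before randomisation and dispensing, worded as a condition in the same way as the pill-count rule. Keep the Visit 2 test, which protects entry to the run-in.

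The cost is one line in the protocol and one more urine test per woman at a visit she already attends. If the sponsor also wants to detect pregnancies that begin during dosing, it could consider repeating the test at Visits 4 and 5; that is a separate choice and is not needed to close the eligibility gap.

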**Visit 3 (Randomization)**

- **Vital Signs:** Weight, Heart Rate, Blood Pressure.
- **Symptom assessment; questionnaires.**
- **Physical Examination**
- **Blood Collection:** General laboratory tests such as complete blood count (CBC) will be performed for all study subjects prior to randomization to ensure the safe and appropriate treatment of subjects. Clinical laboratory tests will be overseen by the PI or a physician sub-investigator. Functional analysis of serum and cells will be measured to look at LPS-binding protein, C-reactive protein (CRP) and a cytokine panel. Serum and cells will be used or banked for translational/mechanistic studies.
- **Stool Sample Collection:** Subject will be provided with a take-home stool collection kit to collect stool samples.
- **Assess pill count:** If pill count from run-in indicates <80% adherence/compliance, subject will not be randomized
- **Randomization:** Subject will be randomized into double-blind portion of the study. Subjects will be given enough study medication to last until next visit.

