**Visit 4 (Day 42, Midpoint)**

- **Symptom assessment; questionnaires.**

- **Physical Examination**
- **Blood Collection:** Serum and cells will be used or banked for translational/mechanistic studies.
- **Stool Sample Collection:** Subject will be provided with a take-home stool collection kit to collect stool samples.
- **Review of concomitant medication use.**
- Subjects will be given enough study medication to last until next visit.

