**Visit 6 (Day 92, at home follow-up)**

- **Symptom assessment; questionnaires.**

Cara App

The app used for the study is called Cara. It is available to the general public via the standard Apple app store. It uses encrypted transmission via HTTPS to transmit data from individuals to a cloud. Their cloud is provided by Microsoft Azur. The app as well as the sponsor will have access to the data.

Questionnaires**Irritable Bowel Symptom Severity Scale (IBS-SSS)**

IBS Severity Scoring System (IBS-SSS) is a widely used questionnaire to assess the symptom severity. It measures abdominal pain intensity, abdominal pain frequency, abdominal distension, dissatisfaction with bowel habits, and influence of IBS on life in general ("life interference") during the preceding week on a 0-100 scale, with the total IBS-SSS score ranging between 0 and 500, with higher scores indicating more severe symptoms.

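### Stool kits go home with the double-blind capsules at Visit 3 and are reissued at Day 84, so the baseline sample can follow active dosing and the end-of-treatment sample will probably follow the last dose

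*Combined protocol and SAP*

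**What the plan says.** All references are to the Combined protocol and SAP, section B3.A.

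- **Screening and Visit 2.** No stool kit is listed at either. Visit 2 starts the placebo run-in: "Subjects will be provided with a single-blind placebo for a period of 28 days pre-randomization".
- **Visit 3 (Randomization).** Capsules: "Subject will be randomized into double-blind portion of the study. Subjects will be given enough study medication to last until next visit". Stool, at the same visit: "Subject will be provided with a take-home stool collection kit to collect stool samples".
- **Visit 4 (Day 42).** The same stool sentence, and capsules dispensed to cover the time to Visit 5.
- **Visit 5 (Day 84).** The same stool sentence. No capsules are dispensed.
- **Visit 6 (Day 92).** An at-home contact that lists symptom assessment and questionnaires only.

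The Study Design paragraph gives the treatment length: "50 IBS-C or IBS-M patients will receive the daily synbiotic for 12 weeks". No visit states a collection day, a rule on sample timing relative to dosing, or how and when a kit is returned. The title puts the stool measure first among the objectives: to "evaluate the impact of a multi-strain synbiotic on fecal metagenomic stability, gut barrier integrity, and metabolic output of the gut microbiota".

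**The concern.** Metagenomic stability is naturally read as a comparison within one woman over time, so it needs one sample clearly before treatment and one clearly on treatment. The visit schedule guarantees neither end. A participant can start her capsules on the day of Visit 3 and use the kit whenever she next passes stool, or later. At Day 84 she receives a kit just as her planned supply runs out.

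Samples in the placebo arm do not change with this timing; samples in the active arm can. The error is therefore differential by arm, and neither randomisation nor blinding removes it. It would tend to shrink or distort the between-arm difference in change. A contaminated baseline also carries into the Day 42 comparison with baseline. Blood is drawn at Visit 3 itself, so baseline blood and baseline stool may fall on opposite sides of the first dose. Once active capsules have been taken, no analysis can recover a pre-treatment sample.

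**Working it through.** The plan gives no figure on this point to reproduce. The check is a timeline, followed by an illustration on stated assumptions.

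**Timeline**

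1. Planned treatment is 12 × 7 = 84 days, which matches Visit 5 at Day 84.
2. Capsules are last dispensed at Visit 4, to cover the time to Visit 5. A kit first handed over at Visit 5 can be used only from Day 84 onward, when planned dosing is ending or over.
3. The delay after Visit 5 has no stated limit. The next listed contact is 92 − 84 = 8 days later and mentions no stool.
4. The Visit 3 kit has no stated limit either. If kits came back at the next visit (an assumption), the sample called baseline could follow anything from 0 to about 42 daily doses.

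**Two readings of the kit sentence**

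| Kit issued at | If used soon after the visit | If used before the next visit |
|---|---|---|
| Visit 3 | Baseline, possibly after the first dose | On treatment |
| Visit 4 | Day 42, on treatment | End of treatment, on treatment |
| Visit 5 | End of treatment, probably after the last dose | After treatment |

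The right-hand reading repairs the Day 84 sample but leaves no baseline.

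**Illustration of size**

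Assumptions, none of them from the documents: the product signal rises and falls exponentially with the same time constant τ; it is at plateau by the end of treatment; dosing starts at Visit 3 and stops at Visit 5; and the sample is collected L days after the visit.

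- Baseline contamination, as a fraction of the plateau: 1 − exp(−L/τ)
- Signal remaining at the end-of-treatment sample: exp(−L/τ)
- Retained change if only one end is affected: exp(−L/τ)
- Retained change if both ends are affected: exp(−L/τ) − [1 − exp(−L/τ)] = 2·exp(−L/τ) − 1

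For example, with τ = 7 and L = 2, exp(−2/7) = 0.75: one end retains 75%, and both ends retain 2 × 0.7515 − 1 = 50%.

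| τ (days) | One end, L = 1, 2, 3 | Both ends, L = 1, 2, 3 |
|---|---|---|
| 3 | 72%, 51%, 37% | 43%, 3%, −26% |
| 7 | 87%, 75%, 65% | 73%, 50%, 30% |
| 14 | 93%, 87%, 81% | 86%, 73%, 61% |

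The one-end column is also roughly what applies to Day 42 against a contaminated baseline, because the Day 42 sample is still on treatment.

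A lag of 1 to 3 days is plausible. The *B. longum* BB536 study in section B2 reports 0.54 ± 0.18 defecations per day in mildly constipated volunteers, or one per 1/0.54 = 1.9 days, and one per 1/0.36 = 2.8 days at one SD below the mean. That is not the trial population, so it supports the range only loosely.

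**The case against.** **The Day 84 sample need not be off treatment.** A reader might infer that the last sample is certainly taken in washout. The text does not go that far. The wording "Subjects will be given enough study medication to last until next visit" sets a minimum supply and does not say that no capsules remain. No visit window, day-numbering convention or last-dose time is given. A dose taken later on Day 84 could follow the sample, and a sample the next morning may be only hours after the last capsule. This stands: the sample is likely, not certain, to follow the last dose.

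**The illustration can be made to look too severe.** A reader might infer that the trial would lose or reverse its stool effect. The negative value arises only with the shortest time constant, the longest lag and both errors in full. Every input is assumed, and the model follows a product signal, whereas the protocol never defines stability. This stands too, which is why the one-end figures are shown alongside.

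**The damage is partial.** The Day 42 sample is on treatment, and a between-arm comparison at that visit needs no baseline. Statistical Considerations names no primary endpoint and no change-from-baseline stool analysis, so a place in the title does not make stool the primary outcome. Symptom outcomes are untouched. All of this is fair, but none of it supplies a pre-treatment sample, and without one a within-person change from the untreated state cannot be relied on.

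**Sites may collect before dosing in practice.** They may, but nothing written requires it, and without recorded sample and dose times the affected samples could not be identified reliably afterwards.

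**Conclusion.** The concern holds, more firmly for baseline than for Day 84. As written, no pre-treatment stool sample is guaranteed: under one reading the baseline can follow active dosing, and under the other it does not exist. On the first of these readings the end-of-treatment sample will probably follow the last dose, by an interval that could be hours or days.

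The likely direction is a smaller or distorted between-arm difference in change. The documents do not give its size. Over lags of 1 to 3 days, the assumed model retains 72% to 37% (τ = 3 days), 87% to 65% (τ = 7) or 93% to 81% (τ = 14) of the true change with an error at one end, and 43% to −26%, 73% to 30% or 86% to 61% with errors at both. These figures show how sensitive the result is to timing; they are not estimates for this product. The matter should be settled before randomisation starts, because a missed baseline cannot be recovered.

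**What to change.** 1. Issue each kit one visit earlier: Visit 2 for baseline, Visit 3 for Day 42, Visit 4 for Day 84.
2. Require the baseline sample late in the placebo run-in and before the first double-blind capsule.
3. Require the end-of-treatment sample while capsules are still being taken, in a stated window before Visit 5.
4. Record the date and time of each sample and of the first and last dose, and state how kits are returned.
5. Report out-of-window samples, with a supportive sensitivity analysis that excludes them. Note that this analysis conditions on behaviour after randomisation, so it should not replace the main comparison.

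**Cost.** A short amendment and a site instruction, with no extra visits or samples. Some kits will be wasted on women who are not randomised after the run-in (placebo responders and those under 80% adherence); the documents give no rate, so the number is unknown. A late baseline sample, which is plausible in women with constipation, may briefly delay the first dose.
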